Abbreviations: Clinical Global Impression of Change (CGI-C); Columbia-Suicide Severity Rating Scale (C-SSRS); electrocardiogram (ECG); End of Study (EoS); Early Termination (ET); Follow-up (F/U); Huntington Disease Quality of Life Questionnaire (HDQoL); Open-label Extension (OLE); Physical Examination (PE); Problem Behaviors Assessment—Short Form (PBA-s); Symbol Digit Modalities Test (SDMT); Stroop Word Reading (SWR); Total Functional Capacity (TFC); Total Motor Score (TMS); Unified Huntington Disease Rating Scale (UHDRS); Visit (V); women of childbearing potential (W●CBP).

Table Footnotes:

[figure not shown]
[figure not shown]
- The OLE VI is the same as Main Study V8 (or V7/W65 for the last group of participants in the Main Study). Assessments do not need to be repeated if conducted as part of the Main Study.
- A participant who discontinues study drug at any point during the OLE, must also be withdrawn from the study and attend an EoS visit.
- In-clinic visit window can be expanded to ±28 days; this applies to all in-clinic visits including OLE V1-4+ and OLE F/U. The expansion of the in-clinic visit window is only in case of a global pandemic.
- Collect blood after ECG is administered (not before).
- Urinalysis will be done as part of Main Study V8, not as part of OLE
- Triple ECG pre-dose.
- Single ECG 1-2 hours post-dose.
- Single ECG pre-dose.

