
 To evaluate the safety and tolerability of pridopidine in participants with HD 	
 Incidence (count and rate) of AEs and serious AEs (SAEs) overall, by severity, by relationship to study drug, and those that led to discontinuation of study drug and/or withdrawal from the study Incidence and shifts of clinically significant abnormalities in electrocardiogram (ECG) (refer to Section 7.1.1), laboratory tests, vital signs, and abnormalities in physical and neurological exam Analysis of Columbia-Suicide Severity Rating Scale (C-SSRS) throughout the study Tolerability: 
 The number (%) of participants who complete the Treatment period The number (%) of participants who fail to complete the Treatment period due to AEs The number (%) of participants who fail to complete the Treatment period due to meeting the Fridericia-corrected QT interval (QTcF) change, CrCl or Psychiatric Stopping Rules
--	--

Exploratory	

 To evaluate the exploratory efficacy effects of pridopidine in participants with HD 	
 Change from Baseline to Weeks 26, 52, 65 and 78 in: 
 Problem Behaviors Assessment - Short Form (PBA-s) total score 
 PBA-s sub-score for apathy Measurement of quality of life using HDQoL

 To evaluate changes in disease biomarker plasma neurofilament light chain (NFL) following treatment with pridopidine in participants with HD 	
 Change from Baseline to Weeks 26, 52, 65 and 78 in plasma NFL protein Relationship between Baseline NFL and changes from Baseline in select efficacy endpoints Relationship between changes from Baseline to Weeks 26, 52, 65 and 78 in NFL and selected efficacy endpoints Proportion of participants with different thresholds for change from Baseline in plasma NFL levels to Weeks 26, 52, 65 and 78

 To evaluate the pharmacokinetics (PK) of pridopidine and its main metabolite in participants with HD 	
 Plasma concentrations of pridopidine and its main metabolite at Weeks 26, 52, 65, and 78 and at last participants' visit Relationship between plasma concentration of pridopidine and clinical outcome measures

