7.2. Discontinuation of Study Drug

In rare instances, it may be necessary for a participant to permanently discontinue (definitive discontinuation) study drug. A participant may discontinue study drug for reasons including but not limited to:

- AE
- Death
- Lost to follow-up
- Non-compliance with study drug
- Physician decision
- Pregnancy
- Protocol deviation
- Study terminated by Sponsor
- Withdrawal of consent by participant
- Loss of capability to consent

The reason for participant discontinuation from the study drug will be recorded in the eCRF.

Participants who are **discontinued from study drug** during the Main Study will be encouraged to continue their participation in the study and perform all the scheduled visits and assessments, while off study drug. If participants are unable/unwilling to attend in-clinic visits, these visits can be replaced with virtual phone visits except for the following: Main Study Week 65, Week 78/EoS and ET visits. If a clinic visit is replaced by a virtual visit at Week 4, Week 26, Week 39, and Week 52, the UHDRS-TFC, clinical laboratories, and vital signs should not be assessed (refer to Appendix 10, Section 10.10). They will continue to be closely monitored by the Investigator and will be referred for psychiatric evaluation per the Investigator's medical judgment. Participants who are discontinued from study drug during the OLE will be withdrawn from the study and will be requested to return to an EoS visit.

See the SoA (Table 2 – Main Study, and Table 3 – OLE) for data to be collected at the time of study drug discontinuation and follow-up and for any further evaluations that need to be completed.

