7.3. Participant Withdrawal from the Study

A participant may withdraw from the study at any time at his/her own request or may be discontinued by the Investigator. Participants may be withdrawn from the study for any of the following reasons:

- Death
- Withdrawal by participant
- Lost to follow-up
- Study terminated by Sponsor

The reason for participant withdrawal from the study will be recorded on the eCRF. At the time of withdrawal, ET visit procedures outlined in the SoA ([Table 2 – Main Study](#), and [Table 3 – OLE](#)) should be completed, if possible.

If the participant withdraws consent for disclosure of future information, the Sponsor may retain and continue to use any data collected, based on local regulations, before such a withdrawal of consent. Participants withdrawing consent may request destruction of any samples taken and not tested, and the Investigator must document this request and proof of destruction in the site study records.

If a participant withdraws from the study, he/she may request the destruction of any samples taken and not tested, and the Investigator must document this in the site study records.

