8.4. Adverse Events

All AEs will be coded using MedDRA Version 23.0 (or a later version if updated during the study).

For statistical analysis, a TEAE is defined as an AE that occurs for the first time or worsens (as captured on the eCRF) on or after initiation of treatment in the corresponding analysis period (Main Study or OLE Treatment Period) EoS. Due to the short half-life of Pridopidine (10-12 hrs) AEs that started more than 14 days after end of treatment are not considered TEAEs.

The terms AEs and TEAEs are used interchangeably in this SAP and unless otherwise specified refer to TEAEs.

An overall summary will be presented by treatment groups that includes the number and percentage of participants who experienced at least one TEAE for the following categories: All TEAEs, serious TEAEs, TEAEs leading to study discontinuation, TEAEs leading to death, TEAEs based on maximal Severity, TEAEs leading to study drug withdrawal anytime during the study, TEAEs leading to study drug withdrawal during titration. When appropriate, a total column may appear as the last column.

Summaries will be presented for all TEAEs by SOC and PT for the following categories of TEAEs:

- TEAEs, severe TEAEs, Treatment-related TEAEs, Serious TEAEs (see below for more details), TEAEs potentially related to QT prolongation, (e.g., palpitations, dizziness, syncope, cardiac arrhythmias, and sudden death), TEAEs related to abuse potential (See Appendix 12.2 for the AE terms), TEAEs causing discontinuation from the study.

The above summaries will include the number of events as well as number and percentage of participants experiencing at least one TEAE in each SOC and PT. To count the number of participants with any TEAEs, a participant who experiences multiple TEAEs within the same SOC will be counted only once for that SOC (if the TEAEs are coded to the same PT). A participant who experiences multiple TEAEs coded to the same PT within the same SOC will be counted only once for that PT. The number and percentage of participants experiencing any TEAE will also be provided. All percentages will use the number of participants in the SP within that treatment group as the denominator. In the summaries SOCs will be sorted in descending order based on number of participants in Total column; PT within SOC will be sorted by descending number of participants in Total column.

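### SAP 8.4 plans no SOC/PT table of TEAEs leading to study drug withdrawal, so AE-driven drug stops in Main Study participants who stay in follow-up are not shown by term and arm

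*SAP*

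**What the plan says.** SAP 8.4 describes two levels of adverse event output.

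- **Overall summary by arm.** It has separate lines for "TEAEs leading to study discontinuation", "TEAEs leading to study drug withdrawal anytime during the study" and "TEAEs leading to study drug withdrawal during titration". The SAP therefore treats leaving the study and stopping drug as distinct outcomes.
- **Tables by SOC and PT.** The list has seven categories: all, severe, treatment-related, serious, QT-related, abuse-related, and "TEAEs causing discontinuation from the study". None is for study drug withdrawal.

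Section 8.4 closes with a listing of TEAEs leading to discontinuation and does not say of what.

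The protocol's safety endpoint in 3.1.1 covers adverse events overall and "those that led to discontinuation of study drug and/or withdrawal from the study". SAP section 2 likewise names both study treatment and study. Protocol 7.2 puts AE first among the reasons for stopping drug and says that Main Study participants who stop "will be encouraged to continue their participation in the study and perform all the scheduled visits and assessments, while off study drug". The OLE differs. The footnote to the schedule in protocol 1.3.2 states: "A participant who discontinues study drug at any point during the OLE, must also be withdrawn from the study".

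**The concern.** The Main Study is built to keep people in follow-up after they stop drug. Protocol 4.1 repeats the encouragement to stay. SAP 5.5.7 counts a participant as a Week 65 completer whether or not they were still taking drug. The treatment policy strategy for the primary endpoint depends on data collected after drug was stopped. In such a design the usual marker of poor tolerability is an event that makes someone stop drug, and a by-term table keyed to leaving the study captures only part of it. The better retention works, the fewer AE-driven drug stops reach that table.

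At stake is a standard safety display. A reader of the report would see how many participants in each arm stopped drug because of a TEAE, but no planned table would show which preferred terms were responsible.

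**Working it through.** The plan states no figure on this point, so the check is a comparison of the texts, followed by a bound on size.

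1. **Which outputs carry the drug-withdrawal attribute?** In the SAP 8.4 overall summary it has two lines, one for any time and one for titration. In the SOC/PT list it appears in 0 of 7 categories.

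2. **Do the two outcomes coincide?** In the OLE they do, because stopping drug requires withdrawal from the study. In the Main Study they do not, because protocol 7.2 encourages participants to stay. The gap therefore lies in the Main Study, among those who stop drug for an AE and remain.

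3. **Does the endpoint ask for both?** Yes, in protocol 3.1.1 and in SAP section 2.

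4. **Does another output fill the gap?**
   - The all-TEAE SOC/PT table contains these events but does not show which led to stopping drug.
   - Disposition (SAP 6.1) gives reasons for withdrawal from treatment or study, not preferred terms.
   - The tolerability endpoints (SAP 3.2.8) count participants who failed to complete treatment because of an AE or a stopping rule. They give no terms either.
   - The listing may include these events, but its wording leaves that open, and a listing does not tabulate incidence by arm.

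5. **Is the terminology stable?** No. For low creatinine clearance, the risk table in protocol 2.3.1 speaks of discontinuation from the study, while 7.1.2 speaks of discontinuation from study drug. The SAP 8.4 category may reflect the same looseness.

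6. **How many participants?** Let N be the number randomized, r the share who stop drug for an AE, and s the share of those who stay in the study. The number missed is N × r × s.
   - N is 480 planned (protocol 4.1) or 499 randomized (SAP revision history).
   - r is not given. The 22.5% dropout rate in SAP 3.3 is not split by reason. I assume 3-8%.
   - s is not given and can lie anywhere from 0 to 1.
   - N × r: 480 × 0.03 = 14.4 and 499 × 0.08 = 39.9, so about 14 to 40 participants stop drug for an AE.
   - Missed: none if s = 0, and all 14 to 40 if s = 1.

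**The case against.** The strongest reply is that most of the information is reported elsewhere. The overall summary gives drug-withdrawal counts by arm. Failures to complete treatment under the QTcF, creatinine clearance or psychiatric stopping rules have their own tolerability count, QT-related TEAEs have their own SOC/PT table, and disposition gives reasons. The listing is not limited to study exit, and SAP 5.1 requires listings to show treatment group, so a reader could count by hand. The category may also simply be loose wording for study drug. All of this stands, and it limits the consequence. It does not supply a by-term, by-arm table of events that led to stopping drug. If study drug was meant, the text still needs correcting.

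Three stronger readings are tempting, and the documents do not support them.

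- **That the protocol never treats study withdrawal as a result of an AE.** Protocol 7.3 introduces its list with "Participants may be withdrawn from the study for any of the following reasons" and names death, withdrawal by participant, loss to follow-up and sponsor termination. However, the endpoint in 3.1.1 expressly includes AEs that led to study withdrawal, 7.3 also allows the investigator to discontinue a participant, and an AE-driven exit could be recorded as the participant's own withdrawal.
- **That the Main Study table would hold little beyond fatal events.** This depends on the first reading. Participants are only encouraged to stay, and someone who stops drug for an AE and then leaves can appear in the table.
- **That the table would make tolerability look worse in the OLE than in the Main Study.** SAP 8.1 presents the two periods separately, and no side-by-side comparison is planned.

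**Conclusion.** The point holds as a missing category. SAP 8.4 separates drug withdrawal from study discontinuation in its overall summary, then gives by-term detail only for study discontinuation. AEs that led Main Study participants to stop drug while staying in the study are not tabulated by term and arm as leading to drug discontinuation, although the endpoint covers them.

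The size cannot be derived from the documents. The figure of about 14 to 40 participants who stop drug for an AE rests entirely on an assumed rate of 3-8%, and the number missed is whatever part of that group remains in follow-up. The gap is descriptive. It leaves the primary and secondary efficacy inference untouched, but it should be closed because the display serves a stated safety endpoint.

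**What to change.** - Add TEAEs leading to study drug withdrawal to the SOC/PT list in SAP 8.4, for both the Main Study and the OLE.
- Keep the existing study-withdrawal table as a separate category. Replacing it would remove by-term detail for the other outcome named in the endpoint.
- State that the discontinuation listing covers study drug withdrawal, with a flag for study withdrawal.
- Reconcile protocol 2.3.1 with 7.1.2 on whether low creatinine clearance leads to discontinuation from the study or from study drug.

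The SAP cost is one added line, one clarified sentence and one further table for each period. The table uses the same data on AEs and drug withdrawal that the overall summary already needs. The creatinine clearance wording is a separate protocol clarification.

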8.5. Deaths

If any participant dies during the study all relevant information will be discussed in the participant's narrative included in CSR.

8.6. Clinical Laboratory Tests

All analysis of clinical laboratory tests will be performed using data from the central laboratory.

Summary statistics for chemistry, hematology, and urinalysis laboratory tests will be presented at Screening, Baseline, Weeks 4, 26, 39, 52, 65, and 78. All test results and associated normal ranges will be reported in the standard International System of Units (SI unit).

Continuous values will be summarized using descriptive statistics by treatment group. Laboratory parameters which have an upper and/or lower reference range: Number and percentage of participants with 6 categories (missing, clinically significant low, not clinically significant low, normal, not clinically significant high, clinically significant high) values at each visit for each parameter will be summarized by treatment group. If a participant has both low and high abnormalities, they will be displayed in both low and high categories based on worst low and worst high values.

Change from Baseline for continuous values will be summarized using both continuous summary statistics as well as shift tables based on normal ranges at each post-baseline visit.

Shift from Baseline (i.e., the distribution of the 5 response categories, category missing will be excluded for readability) tables will include shift from Baseline to each post-baseline visit and the worst post-baseline value across all visits.

The incidence of clinically significant (CS) abnormal values (defined in [Table 4](#)) will be summarized for laboratory data.

Participants with CrCl <30 mL/min, calculated using the Cockcroft-Gault equation $[(140 - \text{age}) \times \text{mass (kg)} \times [0.85 \text{ if female}]] / 72 \times \text{serum creatinine (mg/dL)}$, at any timepoint after the Baseline visit 2 will be summarized.

Table 4: Criteria for Clinically Significant Laboratory Values

Laboratory Parameters	SI Units	Definition of Clinically Significant Values	
Serum Chemistry		Low	High
Liver Function			
Alanine aminotransferase (ALT)			>3 x ULN
Aspartate aminotransferase (AST)			>3 x ULN
Alkaline phosphatase (ALP)			>3 x ULN
Gamma-glutamyl transpeptidase (GGT)			>3 x ULN
Albumin	g/L	<31	
Lactate dehydrogenase (LDH)			>3 x ULN
Total bilirubin			>3 x ULN
Renal Function			
Bicarbonate	mmol/L	<18	
Blood urea nitrogen (BUN)	mmol/L		>14
Creatinine	µmol/L		>3 x Baseline
Creatinine clearance	mL/sec	<0.5 (<30 mL/min)	

General Chemistry			
Calcium	mmol/L	<2.0	>2.74
Chloride	mmol/L	<88	>112
Potassium	mmol/L	<3.4	>6.0
Hematology		Low	High
Hemoglobin (Males)	mmol/L	<7.76 (<12.5 g/dL)	>11.92 (>19.2 g/dL)
Hemoglobin (Females)	mmol/L	<6.83 (<11.0 g/dL)	>10.98 (>17.7 g/dL)
White blood cell counts (WBC)	$10^9/L$	<3	>20
Lymphocytes	$10^9/L$	<0.75	>10
Neutrophils	$10^9/L$	<1	
Eosinophils	$10^9/L$		>1.5
Platelet	$10^9/L$	<75	>700

Box plots will be presented for laboratory parameters listed in [Table 4](#) by visit. Evaluation of drug-induced liver injury will be performed and displayed in eDISH figure which is a log/log scatter plot of peak total bilirubin vs ALT or AST, both in multiples of ULN, with horizontal and vertical lines indicating Hy's law thresholds (i.e., ALT=3 x ULN, AST=3 x ULN, and total bilirubin=2 x ULN).

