8.2.4. Clinical Safety Laboratory Assessments

- See Appendix 2 (Section 10.2) for the list of clinical laboratory tests to be performed and the SoA ([Table 2](#) – Main Study, and [Table 3](#) – OLE) for the timing and frequency.
- The Investigator must review the laboratory report, document this review, and record any clinically relevant changes occurring during the study in the AE section of the eCRF. The laboratory reports must be filed with the source documents. Clinically significant abnormal laboratory findings are those which are not associated with the underlying disease, unless judged by the Investigator to be more severe than expected for the participant's condition.
- All laboratory tests with values considered clinically significantly abnormal during participation in the study should be repeated until the values return to normal or baseline or are no longer considered clinically significant by the Investigator or study Medical Monitor (or designee).
 - If such values do not return to normal/baseline within a period of time judged reasonable by the Investigator, the etiology should be identified, and the Medical Monitor notified.
 - All protocol-required laboratory assessments, as defined in Appendix 2 (Section 10.2), must be conducted in accordance with the Laboratory Manual and the SoA.
 - If laboratory values from non-protocol specified laboratory assessments, performed at the institution's local laboratory, require a change in participant management or are considered clinically significant by the Investigator (e.g., SAE or AE or dose modification), then the results must be recorded in the eCRF.
- Home visits by health care professionals may be provided for safety blood draws if clinic visits will not be possible. Note, this will only occur if the nursing service is activated during COVID-19 and the participant is on treatment.

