10.2. Appendix 2: Clinical Laboratory Tests

- The tests detailed in [Table 7](#) will be performed by the central laboratory (unless otherwise indicated).
- Protocol-specific requirements for inclusion or exclusion of participants are detailed in Section [5](#) of the protocol.
- Additional tests may be performed at any time during the study as determined necessary by the Investigator or required by local regulations.
- Investigators must document their review of each laboratory safety report in participant's source records.

Table 7: Protocol-Required Safety Laboratory Assessments

Laboratory	Parameters – Main Study	Parameters - OLE
Serum Chemistry	Calcium, phosphorus, sodium, potassium, chloride, magnesium, bicarbonate, creatinine, blood urea nitrogen (BUN), creatine kinase, uric acid, glucose, cholesterol, triglycerides, lactate dehydrogenase (LDH), alkaline phosphatase, ALT, AST, indirect bilirubin, total bilirubin, direct bilirubin, GGT, total protein, albumin, globulin, total protein, albumin	Calcium, phosphorus, sodium, potassium, chloride, magnesium, bicarbonate, creatinine, BUN, glucose, LDH, alkaline phosphatase, ALT, AST, indirect bilirubin, total bilirubin, direct bilirubin, GGT, total protein, albumin
Hematology	Hemoglobin, hematocrit, RBC, MCH, MCHC, MCV, RDW, RBC morphology, platelet, WBC (neutrophils, lymphocytes, eosinophils, monocytes, basophil)	Hemoglobin, hematocrit, RBC, MCH, MCHC, MCV, RDW, RBC morphology, platelet, WBC (neutrophils, lymphocytes, eosinophils, monocytes, basophil)
Urinalysis	Protein, glucose, ketones, bilirubin, urobilinogen, hemoglobin, pH, specific gravity, appearance, color, leukocyte esterase, nitrite, microscopic tests (bacteria, erythrocytes, leucocytes, crystals, casts, epithelial cells, yeast, oval fat bodies, fat, mucous, sperm, trichomonas)	None
Other laboratory assessments	β-HCG pregnancy test (as needed for women of childbearing potential) Urine pregnancy	β-HCG pregnancy test (as needed for women of childbearing potential) Urine pregnancy

10.3. Appendix 3: Adverse Events: Definitions and Procedures for Recording, Evaluating, Follow-up and Reporting

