- To maintain the integrity of the study, alternative methods of collecting study procedures may be considered where possible and in certain situations, with Sponsor approval:
 - Four Virtual visits have been incorporated as part of the study in addition to on site clinic visits and safety phone visits. Remote study assessments can be completed virtually (via telephone).
 - If on site clinic visits are not possible the visits can be converted to virtual visits (except Screening, Baseline and Week 65) (via telephone).
 - Study assessments will only be conducted in a remote manner if they can be done without affecting the wellbeing of the participant during the study and with the same level of scientific integrity as assessments conducted in a physical study center.
 - According to site operations during public health pandemics, home visits by a health care professional may be used to collect laboratory samples, obtain an ECG, and perform assessments as required by the protocol.
 - A local laboratory may be used to collect laboratory samples as required by the protocol. Local analysis can be used for safety decisions. In addition, a local laboratory can be used for study endpoints if samples drawn at the local laboratory cannot be shipped to the central laboratory. If a local laboratory is used, applicable lab ranges and laboratory certification should be provided to the Sponsor.
 - Data collected from participants participating in remote visits/assessments-may be collected electronically using purpose-built technology, or via traditional paper-based methods. AE/SAE (reporting, assessing and follow-ups) will be handled similarly to a traditional model, with the participant contacting study personnel or engaging local care for public health emergencies.
 - In cases where a participant is continuing to receive study drug but COVID-19 pandemic-related circumstances preclude a visit to the investigative site, remote visits (e.g., virtual visits via telephone) will be allowed for relevant study

procedures while maintaining participant's privacy, as would be done for a clinic visit.

- For missed assessments for primary and secondary endpoints, please discuss these situations with the Sponsor for approval. In certain situations, with prior approval, other options or delayed visits, can be considered.

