5.4. Data Presentation Conventions

Continuous variables (e.g., age) are summarized using descriptive statistics (the number of participants with available data, the mean, SD, first quartile (Q1), median, third quartile (Q3), minimum and maximum). Categorical variables (e.g., race) are summarized using counts and percentages. Percentages are calculated using the total participants per treatment group with available data (overall or within relevant subgroup when appropriate). Summaries for discrete variables will include frequencies and percentages. Unless obvious, denominators used for computation of percentages will be indicated in footnotes on tables.

The following conventions will be applied to all data presentations and summaries.

- For continuous variables, all mean, Q1 (25th percentile), median and Q3 (75th percentile) values are formatted to one more decimal place than the measured value. SD values are formatted to two more decimal places than the measured value. Minimum and maximum values are presented with the same number of decimal places as the measured value. This rule may be modified to fit data in a given table as long as the data displays relevant decimal places for interpretation of results.
- For categorical variables, the number and percentage of responses are presented in the form XX (XX.X%) where the percentage is in the parentheses and will be rounded to one decimal place.
- Date variables are formatted as DDMMYYYY for presentation. Time is formatted in military time as HH:MM for presentation.
- Wherever possible, data will be decimal-centered, or left aligned as appropriate to best display the data and column headers. Parentheses will also be aligned appropriately for best display. This will be detailed in the mock shells.
- P-values, if applicable, will be presented to 4 decimal places. If the p-value is less than 0.001 then it will be presented as <0.001. If the rounded result is a value of 1.000, it will be displayed as >0.999.
- Summaries of clinically significant abnormal values will include all post-baseline values (including scheduled, unscheduled, and ET visits).
- Unless otherwise stated, any statistical tests performed will use 2-sided tests at the 5% significance level.

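### SAP 8.6 admits only central-laboratory data, so a threshold-crossing or peak value measured only at a local laboratory can be missing from the abnormality, worst-shift, creatinine-clearance and liver-injury outputs

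*SAP*

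**What the plan says.** SAP Section 8.6 sets one data source for the whole laboratory section: "All analysis of clinical laboratory tests will be performed using data from the central laboratory". The same section defines the incidence of clinically significant values (Table 4), shifts to the worst post-baseline value, a summary of participants whose CrCl falls below 30 mL/min at any time after Baseline, and an eDISH plot of peak bilirubin against ALT or AST in multiples of the upper limit of normal (ULN).

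The protocol makes central testing the default (Section 10.2) but provides two routes by which local results arise.

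- **Section 10.10 (pandemic guidance).** "A local laboratory may be used to collect laboratory samples as required by the protocol", and "Local analysis can be used for safety decisions". Further, "a local laboratory can be used for study endpoints if samples drawn at the local laboratory cannot be shipped to the central laboratory". These are alternatives for certain situations and need Sponsor approval. Local reference ranges are to be sent to the Sponsor.
- **Section 8.2.4.** Results of tests outside the protocol's own set, run at the institution's laboratory, must be entered in the eCRF if they "require a change in participant management or are considered clinically significant by the Investigator".

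SAP Section 3.6.2 repeats that local laboratories may be used for safety tests. No SAP section says how those results are analysed. The SAP Preface makes the SAP prevail where it differs from the protocol.

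**The concern.** By-visit means and changes gain from a single assay and a single set of ranges, so a central-only rule suits them. Threshold and peak displays ask something else: did this participant ever cross the line, and how far? For that question, excluding a source of valid results can only lower the count or the peak.

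The local values recorded under Section 8.2.4 are kept because they changed management or were judged clinically significant, so they are likely to include extremes. At stake are the laboratory displays for two monitored matters. One is decreased creatinine clearance, which Protocol Section 2.3.1 lists as an identified risk and Section 7.1.2 gives its own stopping rule. The other is possible drug-induced liver injury, where one participant in the upper-right region of the eDISH plot matters to the reader.

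**Working it through.** **1. Plan figure checked.** Table 4 gives the CrCl criterion in two units. 30 mL/min ÷ 60 = 0.5 mL/sec, so they agree. The plan states no figure for local-laboratory use, so there is nothing further to reproduce. The point rests on the text.

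**2. When a local value is lost, output by output, applying SAP 8.6 literally.**

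| SAP 8.6 output | A local result matters if | It is lost or understated only if |
|---|---|---|
| Clinically significant incidence (Table 4) | it crosses the limit | no central sample from that participant crosses it |
| Shift to worst value | it falls in a worse category | no central sample reaches that category |
| CrCl <30 mL/min at any time | it is below 30 | no central CrCl is below 30 |
| eDISH peak | it exceeds every central value | always understated; misplaced relative to the Hy's law lines (ALT or AST 3 × ULN, bilirubin 2 × ULN) only if the central peak is inside them |

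The loss is therefore conditional in every row.

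**3. Do other SAP rules bring the local value back?** SAP Section 5.4 says: "Summaries of clinically significant abnormal values will include all post-baseline values". The sentence goes on to name scheduled, unscheduled and early-termination visits. Section 5.8.4 likewise uses all available data from scheduled and unscheduled visits for abnormality and shift tables. Both decide which visits count; neither names a laboratory. Read with 8.6, they give all central values at any visit. They do not contradict 8.6, and they do not settle the source question either.

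**4. What the documents say about frequency.** SAP Section 3.2 reports that fewer than 2% of scheduled in-clinic visits were missed or lacked a UHDRS-TFC assessment as of September 2022. SAP Section 6.6 reports no important protocol deviations due to COVID-19. Both suggest that the Section 10.10 route was little used. Neither bounds the event-driven tests of Section 8.2.4.

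**5. Illustration under assumptions.** Let K be the number of participants who truly cross a threshold and f the share who do so only on a local value. Neither is in the documents. Treating participants as independent,

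P(at least one case missing) = 1 − (1 − f)^K.

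For K = 3:

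- f = 2%: 1 − 0.98³ = 5.9%
- f = 10%: 1 − 0.90³ = 27.1%
- f = 20%: 1 − 0.80³ = 48.8%
- f = 50%: 1 − 0.50³ = 87.5%

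For a single case (K = 1) the probability is f itself.

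With the planned 240 per arm, exact (Clopper-Pearson) two-sided 95% limits are:

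- 1/240 = 0.42%, 0.01% to 2.30%
- 0/240 = 0%, upper limit 1.53%

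The SAP change log gives 499 randomised, about 250 per arm. Then 1/250 has limits 0.01% to 2.21%, and 0/250 has upper limit 1.46%. These figures describe any single omitted case. They do not estimate how often this rule would omit one.

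**The case against.** The other side has a good case.

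- **Central-only is a coherent rule.** It matches the protocol default. Local values selected by investigators differ in assay, range and ascertainment, and pooling them with systematic central data changes what the table measures. This stands as a reason not to replace the central tables. It is no reason to omit the local values from every threshold display.
- **The signal is not lost to the study.** Protocol Section 8.2.4 requires clinically relevant laboratory changes to be entered on the adverse event page, and they then reach the tables of SAP Section 8.4. This stands. A reader might infer that a local-only case would vanish from safety reporting altogether; the documents do not support that. The gap is in the laboratory outputs. Laboratory listings are not a certain backstop, because SAP Section 5.1 names them as an example of listings that may be dropped by agreement with the agency.
- **Repeats limit the loss.** Clinically significant results must be repeated (Section 8.2.4), and a CrCl below 30 mL/min calls for a return visit one week later (Section 7.1.2). Any central result from such a repeat stays in. This stands for persistent abnormalities and less so for a transient peak.
- **Standardising may fail.** The duty to supply local ranges is in Section 10.10 and is not repeated in 8.2.4, and Cockcroft-Gault needs a body weight. This stands, and the fix allows for it.

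Two other strong readings are tempting. One is that 8.6 contradicts 5.4 and 5.8.4; step 3 of the working shows that it does not. The other is that local draws cluster around acute illness, so the worst values drop out as a matter of course. Neither document says so, and the loss needs the condition in step 2.

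**Conclusion.** The point holds in conditional form. Followed literally, SAP 8.6 can leave a threshold-crossing or peak value measured only locally out of the clinically significant incidence, worst-shift, CrCl and eDISH outputs. The protocol allows such values to guide safety decisions and requires some of them to be in the database. The SAP acknowledges local testing but has no analysis rule for it.

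The size is not determinable from the documents. The pandemic route was probably uncommon; event-driven local testing is unquantified. The conclusion assumes only that 8.6 is applied as worded and that at least some local results have no equivalent central sample. Efficacy is unaffected, and the adverse event tables remain a second path for the same finding. It is worth correcting because one case can change how a rare laboratory finding reads, and the correction is inexpensive.

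**What to change.** Amend SAP 8.6, or use the Addendum route in SAP Section 5 if the database is not yet locked:

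1. Keep central-only data for by-visit descriptive statistics and changes, and for the central versions of all tables.
2. For clinically significant incidence, worst-value shifts, CrCl below 30 mL/min and eDISH, also present results with eCRF-recorded local values included and flagged by source.
3. Convert local results to SI units, express enzymes and bilirubin as multiples of the local ULN where the range is available, and use the nearest recorded weight for CrCl.
4. List separately any local value that cannot be standardised.
5. Add a sentence to SAP 5.4 and 5.8.4 stating which laboratory sources their all-values rules cover.

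The cost is SAP wording, some unit and range harmonisation, and a second version of four outputs. No participant procedure changes. Local values are more variable and selectively ascertained; showing results with and without them lets the reader see how much they matter.
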